1.1. Study Objectives

The purpose of this feasibility study is to use a multimodal approach of general anesthesia supplemented by topical analgesia during flexible bronchoscopy and endobronchial ultrasound. The aim is to determine if the administration of lidocaine via "spray as you go" vs. nebulizer would result in reduced severity of cough during the procedure and maximizing efficient sample acquisition while limiting the amount of general anesthetic given. The use of the vibrating mesh nebulizer is presumed to lead to an even distribution during lidocaine administration and thereby lead to decreased number of severe coughs during procedure improving efficiency of sample acquisition and reduce the dose of general anesthetic required.

1.2. Primary Study Endpoints

The primary endpoint will assess if different modes of lidocaine administration ("spray as you go" vs nebulized vs atomized) decrease the severity of intraoperative coughing. Severe coughs will be identified by the anesthesiologist and bronchoscopist as cough which results in pausing procedure and/or requiring repeated dosing of anesthetic.

1.3. Secondary Study Endpoints

Secondary endpoints will include: additional amount(s) of fentanyl and propofol used to suppress cough during procedure, cough and sore throat post-procedure and time to emergence following the end of the procedure.

2. Background

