2.1. Scientific Background and Gaps

Flexible bronchoscopy and endobronchial ultrasound with transbronchial needle aspiration are the most commonly performed procedures by a pulmonologist when assessing lung disease, mediastinal and hilar lymphadenopathy. A combination of general anesthesia along with topical analgesia is important to maximize patient tolerance while limiting cough. The use of lidocaine as a topical anesthetic has the benefit of reducing the overall depth of the anesthetic with minimal risk of complications related to systemic absorption.

The current consensus statement on analgesia, anesthesia and sedation during bronchoscopy (Chest 2005) recommend sedation with Propofol which allows for shorter patient recovery, analgesia with Fentanyl due to its quick onset of action, rapid peak effect and relatively short duration of effect as well as topical anesthesia using lidocaine to provide the optimal environment for bronchoscopy while also limiting potential risks. Currently however, the optimal mode of administration of topical lidocaine has yet to be determined.

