3.2. Exclusion Criteria

The following exclusion criteria will be used:

- 1. Any intervention beyond flexible bronchoscopy and EBUS/TBNA
- 2. Inability to tolerate bronchoscopy.
- 3. Patients that receive paralytics.
- 4. Patients with neuromuscular diseases.
- 5. Inability to consent for procedures.
- 6. Allergies to lidocaine or any other drugs used in protocol.
- 7. Existing renal insufficiency or liver disease

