7.1. Study Design

Patient is identified and consent is obtained in clinic, hospital room or pre-operative area. In the Same Day Pre-Anesthesia Care Unit they will receive Robitussin DM 20 ml syrup orally (Dextromethorphan 20mg) at least 60 minutes prior to bronchoscopy.

Once in the main procedure room patients will be induced into an anesthetic state using the following medications and dosing ranges. It will be titrated by anesthesiologist at bedside with goal to achieve hypnosis and apnea without profound bradycardia. The duration of the infusion is as required for the duration of the procedure.

- Propofol (1-3 mg/kg bolus and infusion of 50-200 mcg/kg), fentanyl 25-50 mcg on induction and alfentanil as a continuous infusion will be given at a rate of 0.5-2 mcg/kg/min with 1-3 mcg/kg bolus every 2-5min if need for further cough suppression. The Propofol infusion will be titrated to maintain BIS values between 40-60 for the duration of the procedure. When it is anticipated that the procedure will conclude within the next 10 minutes, the Propofol and alfentanil infusions will be stopped.

Contingency Plan: If despite the maximum dose of Propofol (150 mcg/kg/min) and alfentanil the patient continues to cough such that the procedure cannot be carried out, then Rocuronium will be administered IV (dose 20-40 mg at the discretion of the anesthesiologist) and its residual effect will be reversed using neostigmine (20-70 mcg/kg) and glycopyrrolate (10 mcg/kg) at the end of the procedure.

The patient's airway will be managed using a laryngeal mask airway (LMA) (Ambu Aura-I Size 4 or 5). Their airways will be anesthetized using a maximum of 2 mg per kg (max dose 160mg) of lidocaine, administered by one of the following techniques below. Randomization will be completed by selection of unmarked envelope.

- 1. "Spray as you go" 16mL of 1% lidocaine sprayed in 4 mL aliquots. One at the vocal cords, one at midtrachea, one at left main stem bronchus and one at right mainstream bronchus.

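### The secondary drug-use endpoint leaves out alfentanil, the only drug the regimen gives as a bolus expressly for cough

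*Combined protocol and SAP*

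**What the plan says.** Section 1.3 of the combined protocol and SAP lists among the secondary endpoints "additional amount(s) of fentanyl and propofol used to suppress cough during procedure". Two drugs are named.

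Section 7.1 describes three drugs for anesthesia and cough control:

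- Fentanyl and alfentanil: "fentanyl 25-50 mcg on induction and alfentanil as a continuous infusion will be given at a rate of 0.5-2 mcg/kg/min". The alfentanil infusion is supplemented "with 1-3 mcg/kg bolus every 2-5min if need for further cough suppression".
- Propofol, as a bolus and then an infusion: "The Propofol infusion will be titrated to maintain BIS values between 40-60 for the duration of the procedure".
- The contingency plan in the same section begins "If despite the maximum dose of Propofol (150 mcg/kg/min) and alfentanil the patient continues to cough", so it treats both propofol and alfentanil as already in use against persistent cough.

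Two other places refer to anesthetic quantities in general terms. Section 2.3 says that the overall anesthetic dose will be evaluated, and section 16.1 says that an anesthetic quantity will be collected in the procedure room. Neither names a drug or a unit. The list in section 7.1 of what goes into the research record during the procedure covers the BIS average, vasopressor interventions and several times, but no drug amounts. Section 8.3 plans medians and interquartile ranges for continuous variables.

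**The concern.** A drug-use endpoint of this kind is meant to show whether better topical anesthesia spares systemic drug. Section 1.1 makes that an explicit aim: the vibrating mesh nebulizer is expected to lower the dose of general anesthetic needed. The endpoint can show such an effect only if it counts the drugs that the team gives when the patient coughs.

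Set against section 7.1, the drug list in section 1.3 does not match. It omits the one drug whose bolus is expressly triggered by cough, and it includes fentanyl, for which section 7.1 describes no dose after induction. If the arms differ in how much alfentanil is needed for cough, the endpoint analysed as written would not show it. Section 2.3 also says that a difference found here would lead to the sizing of a later superiority study, so it matters that the reported quantities are the relevant ones.

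**Working it through.** The plan states no figure on this point, so the check is mainly a comparison of text.

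**Step 1. Match each drug's role in section 7.1 to the endpoint in section 1.3.**

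| Drug | Role in section 7.1 | Dose expressly tied to cough? | Counted in section 1.3? |
|---|---|---|---|
| Fentanyl | At induction; no later dose described | No | Yes |
| Propofol | Infusion titrated to BIS 40-60; contingency plan implies it may be raised for cough | By implication | Yes |
| Alfentanil | Infusion plus repeat bolus | Yes, the bolus | No |

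The alfentanil row is the mismatch. The propofol row is why the endpoint still carries some information on cough.

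**Step 2. Look for a passage that closes the gap.** Alfentanil is named in section 7.1 and nowhere else; no endpoint and no listed data item mentions it. The general wording in sections 2.3 and 16.1 might include it or might not. Section 2.1 separates sedation from analgesia when it says that consensus guidance would "recommend sedation with Propofol which allows for shorter patient recovery, analgesia with Fentanyl due to its quick onset of action", which could place an opioid outside an anesthetic quantity. Section 7.1, however, groups the opioids with propofol as the drugs that induce the anesthetic state. Both readings are open, so the general wording does not settle what will be reported.

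**Step 3. Size of what is left out.** The inputs are the bolus range of 1-3 mcg/kg and the infusion range of 0.5-2 mcg/kg/min, both from section 7.1.

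- Boluses for cough: with n boluses, the omitted amount is n × 1 to n × 3 mcg/kg. If n = 0, it is 0.
- Infusion: over t minutes the omitted amount is 0.5 × t to 2 × t mcg/kg. At an assumed 30 minutes this is 0.5 × 30 = 15 to 2 × 30 = 60 mcg/kg.

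The documents give neither n nor t, so these expressions show how the omission scales and do not estimate it.

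**Step 4. Does the cough count stand in for the amount?** Only in part. Under section 7.1, a cough that prompts an extra anesthetic dose counts as an event, so a cough-triggered bolus can appear in the count. The amount does not follow from the count: four boluses can total 4 × 1 = 4 or 4 × 3 = 12 mcg/kg, a threefold range.

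**The case against.** The case for leaving the text alone has four parts.

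- **The endpoint list may not be exhaustive.** Section 1.3 introduces the secondary endpoints as ones that will be included, and sections 2.3 and 16.1 promise an anesthetic quantity. That is fair, but an open list with no agent or unit still does not commit the trial to reporting alfentanil.
- **The data may be captured anyway.** The subject forms mentioned in section 10.2 are not in the documents. A reader might infer that alfentanil data will be lost; the documents do not support that. The finding concerns the endpoint definition only.
- **Propofol also responds to cough.** A reader might infer that alfentanil is the main cough drug, or that the endpoint measures nothing relevant. Neither is supported. Section 7.1 does not rank the agents, and its contingency plan names propofol beside alfentanil. Nor does it rule out fentanyl after induction, and section 1.3 itself anticipates additional fentanyl. What stands is narrower: alfentanil is the only agent with a bolus expressly given for cough, and it is not counted.
- **Little depends on it.** The endpoint is secondary and descriptive, in a feasibility study of 48 patients, and no test rests on it. This objection stands, and it sets the size of the point.

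**Conclusion.** The mismatch between sections 1.3 and 7.1 is real and can be seen from the text alone. Analysed as written, the endpoint would miss any difference between arms in alfentanil use, whether from boluses or infusion. It is incomplete rather than empty, because added propofol, and any added fentanyl, would still be counted.

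The point is minor. The amount omitted is 1-3 mcg/kg for each cough bolus, plus the infusion, and it may be small if few boluses are needed. No difference between arms is predicted, since the documents give no expected bolus count. The primary cough count is unaffected.

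The conclusion assumes that section 7.1 describes the regimen actually used and that section 1.3 would be applied literally.

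**What to change.** Reconcile sections 1.3, 2.3, 7.1 and 16.1 so that they refer to the same drugs:

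1. Add alfentanil to the drug-use endpoint in section 1.3, as the amount given in boluses for cough and as the total dose (infusion plus boluses).
2. List the amounts of fentanyl, propofol and alfentanil, with units, among the items recorded under section 7.1. The general references in sections 2.3 and 16.1 then have a defined content.
3. Report each drug separately as median and interquartile range by arm, the format already set in section 8.3.

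The cost is a few form fields and a little descriptive analysis, with no extra patients or visits. The change concerns what is measured and reported; it proposes no dose or clinical rule.

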2.1. Scientific Background and Gaps

Flexible bronchoscopy and endobronchial ultrasound with transbronchial needle aspiration are the most commonly performed procedures by a pulmonologist when assessing lung disease, mediastinal and hilar lymphadenopathy. A combination of general anesthesia along with topical analgesia is important to maximize patient tolerance while limiting cough. The use of lidocaine as a topical anesthetic has the benefit of reducing the overall depth of the anesthetic with minimal risk of complications related to systemic absorption.

The current consensus statement on analgesia, anesthesia and sedation during bronchoscopy (Chest 2005) recommend sedation with Propofol which allows for shorter patient recovery, analgesia with Fentanyl due to its quick onset of action, rapid peak effect and relatively short duration of effect as well as topical anesthesia using lidocaine to provide the optimal environment for bronchoscopy while also limiting potential risks. Currently however, the optimal mode of administration of topical lidocaine has yet to be determined.

2.2. Previous Data

A previous study by Dreher, M., et al. published in Respiration evaluated nebulized versus "spray as you go" application of lidocaine during flexible bronchoscopy. This study selected patients undergoing diagnostic bronchoscopy with endobronchial or transbronchial biopsy. All patients underwent general anesthesia and intubation prior to procedure, then were randomized to a topical lidocaine versus Enk Fiberoptic Atomizer Set. Primary outcomes were the Aldrete score >9 to assess recovery after bronchoscopy and patient perceived tolerance with the visual analogue scale. This study showed no

difference between the two groups, however the primary outcome was patient comfort during procedure and most patients had complete amnesia for the procedure. Bronchoscopist and anesthesiologist evaluation of cough during procedure was not evaluated.

Another study by Stolz D., et al. published in Chest was a prospective, randomized, placebo controlled double blind trial which evaluated whether nebulized lidocaine provides additional benefit and reduces total anesthetic dose required during bronchoscopy in addition to topical lidocaine administration. Primary outcomes including both patient and operator visual analogue score for cough which were similar between groups. This however was not a comparison trial between different administration techniques of the lidocaine and included only flexible bronchoscopy patients, endobronchial ultrasound and biopsy patients were not included.

2.3. Study Rationale

While the procedures of flexible bronchoscopy and endobronchial ultrasound is commonly performed to assess a wide range of lung disease, studies evaluating the mode of administration of topical lidocaine to prevent coughing and improve efficiency of the procedure have not yet been completed. We propose a prospective, randomized, stratified sampling, open label study of topical vs nebulized vs atomized lidocaine during flexible bronchoscopy and endobronchial ultrasound. Postoperative outcome assessors will be blinded to intraoperative therapy. We propose to evaluate the different modes of administration of topical lidocaine and their effect on the number of severe coughs as per anesthesia and the bronchoscopist, total dosing of anesthesia, post-procedure cough and sore throat and complications related to lidocaine.

As there have been no studies in regards to the mode of lidocaine application in bronchoscopy, our study is a feasability study to identify if a difference is present between nebulized and topical groups. If one is identified, we will plan to determine number needed to power a future superiority study.

Inclusion and Exclusion Criteria

3.1. Inclusion Criteria

The following inclusion criteria will be used:

- 1. Diagnosis of mediastinal and/or hilar lymphadenopathy requiring endobronchial ultrasound evaluation and transbronchial needle aspiration.
- 2. Diagnosis of pulmonary disease requiring flexible bronchoscopy
- 3. Greater than 18 years of age.

Vulnerable populations as identified in HRP-412, HRP-413, HRP-414, HRP-415, HRP-416 and HRP-417 will not be included in this study.

3.2. Exclusion Criteria

The following exclusion criteria will be used:

- 1. Any intervention beyond flexible bronchoscopy and EBUS/TBNA
- 2. Inability to tolerate bronchoscopy.
- 3. Patients that receive paralytics.
- 4. Patients with neuromuscular diseases.
- 5. Inability to consent for procedures.
- 6. Allergies to lidocaine or any other drugs used in protocol.
- 7. Existing renal insufficiency or liver disease

3.3. Early Withdrawal of Subjects

3.3.1. Criteria for removal from study

Withdrawn from the study if the bronchoscopy is terminated early due to patient safety concerns. Withdrawn if the subject withdraws consent for the study or the procedure. Subjects will retain the right to withdrawal consent at any time without consequences of any kind, including the right to future treatment.

There are no identified safety concerns, nor concerns of disease progression as this study will not interfere with diagnosis nor treatment. Individuals enrolled in the study will continue to receive treatment consistent with accepted standard of care. Based on study protocol diagnostic and outcome information will be obtained, but will not be used to alter medical decision making.

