3.3.2. Follow-up for withdrawn subjects

Follow up by routine standard of care treatment. The intervention of this study is limited and has no lasting effects therefore long term follow up is not required. Individuals that are withdrawn from the study will continue treatment and follow up visits consistent with standard of care. Currently there is no anticipated need to replace individuals withdrawn from the study as there will be concurrent active recruitment.

4. Recruitment Methods

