- 2. Nebulizer 2 % (preservative free) lidocaine (dose 2mg/kg max dose 160 mg) will be administered via a jet nebulizer, in the operating room over ten minutes, followed by procedure immediately after. The patient will be sitting propped up and his SpO2, EKG and BP will be monitored during this time. The jet nebulizer supply tube will be connected to central oxygen at 6 L/min and the duration of nebulization will be dryness of the nebulizing chamber or max of 10 minutes. [The Salter Series Small Volume Jet Nebulizer will be used.]
- 3. Vibrating Mesh Nebulizer 2 % (preservative free) lidocaine (dose 2mg/kg max dose 160 mg) will be administered via a vibrating mesh nebulizer, in the operating room over ten minutes, followed by procedure immediately after. The patient will be sitting propped up and his SpO2, EKG and BP will be monitored during this time. The jet nebulizer will be

connected to central oxygen at 6 L/min and the duration of nebulization will be dryness of the nebulizing chamber or max of 10 minutes. [The Aerogen Solo Vibrating Mesh Nebulizer will be used.]

Patient will undergo scheduled procedure of flexible bronchoscopy or endobronchial ultrasound examination. During procedure, bronchoscopist and anesthesiologist will count the number of episodes of cough. Cough is defined as a cough which requires intervention such as additional dose of anesthetic or requires a pause in the procedure. During procedure, BIS monitor average, number of vasopressor interventions for MAP <60, induction time, procedure time and wake up time will be documented in the research record.

Following procedure, patient will be brought to post-op anesthesia care unit. Time to discharge readiness will be collected as well as the responses of the patient to the following questions:

- sore throat: absent, mild, moderate, severe
- cough: absent, mild, moderate, severe

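### Subjects whose bronchoscopy is stopped early for safety are withdrawn after randomisation, and nothing in the plan keeps them in the analysis of their assigned arm

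*Combined protocol and SAP*

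**What the plan says.** Section 3.3.1, on removal from the study, gives two grounds and treats them alike. One is withdrawal of consent. The other is a safety stop: "Withdrawn from the study if the bronchoscopy is terminated early due to patient safety concerns". The subject leaves the study, not only the procedure.

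Section 3.3.2 describes what follows: "Follow up by routine standard of care treatment". On numbers it adds: "Currently there is no anticipated need to replace individuals withdrawn from the study as there will be concurrent active recruitment".

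The results at stake are these:

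- The primary endpoint (1.2) rests on severe cough, meaning "cough which results in pausing procedure and/or requiring repeated dosing of anesthetic". Under 7.1 the bronchoscopist and anesthesiologist count such episodes during the procedure.
- Section 2.3 also lists "total dosing of anesthesia, post-procedure cough and sore throat and complications related to lidocaine" among the outcomes to be compared.
- In the recovery unit (7.1), "Time to discharge readiness will be collected as well as the responses of the patient to the following questions". The questions are graded sore throat and graded cough.

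Under 7.4.3 the envelope is opened immediately before the procedure. Section 8.1 assigns 48 patients: 24 topical, 12 jet nebulizer and 12 vibrating mesh nebulizer. Section 8.2 marks sample size determination as not applicable. Section 8.3 plans medians, interquartile ranges and percentages. None of 8.1 to 8.3 says who is analysed, what happens to data collected before withdrawal, or how a stopped procedure counts.

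**The concern.** Because the envelope is opened just before the procedure, every early stop of a bronchoscopy comes after allocation. A safety stop need not be caused by cough or by lidocaine, but it can be, and the technique by which lidocaine was given can affect it. Removing such subjects is therefore a loss after randomisation that may be related to outcome. If they drop out of the tables, the arms compared are no longer the arms randomised, and an arm with more stopped procedures can look better than it was.

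The plan does not settle whether they drop out. The choice could be made after the data are seen, by people who know the allocation: bronchoscopist and anesthesiologist are unblinded (7.4.5), and the principal investigator does the primary analysis (16.3).

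The between-arm difference is the main product of this feasibility study. Section 2.3 uses it to decide whether to plan a superiority trial and how large that trial should be. With 12 subjects in each nebulizer arm, one or two losses matter.

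**Working it through.** **1. The plan's own figure.** 24 + 12 + 12 = 48, as stated in 8.1. There is no sample-size calculation to reproduce, and the plan gives no termination rate, cough rate or variance.

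**2. What happens to each item when a procedure is stopped for safety.**

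| Item | Still collected? | Place in the results |
|---|---|---|
| Safety events | Yes: 10.3, 10.6 and 20.1.2 make no exception for stopped procedures | Not stated for the between-arm complication summary |
| Coughs counted up to the stop | Counted as they occur (7.1) | Not stated |
| Recovery-unit cough, sore throat, discharge readiness | 7.1 makes no exception, but the subject has left the study and 3.3.2 describes routine care only | Not stated |

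**3. Weight of one subject (8.1).** 1/12 = 8.3% of a nebulizer arm; 1/24 = 4.2% of the topical arm.

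**4. Chance of at least one stop.** For n subjects and a true stop rate q this is 1 − (1 − q)^n. The rates are assumptions.

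| Assumed q | n = 12 | n = 24 | n = 48 | Expected stops, 48 × q |
|---|---|---|---|---|
| 1% | 11.4% | 21.4% | 38.3% | 0.48 |
| 2% | 21.5% | 38.4% | 62.1% | 0.96 |
| 5% | 46.0% | 70.8% | 91.5% | 2.4 |
| 10% | 71.8% | 92.0% | 99.4% | 4.8 |

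**5. Effect on a percentage, if stopped subjects were left out.** Assume that one third of each arm has severe cough and that the stopped subjects are among them.

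- Nebulizer arm, all kept: 4/12 = 33.3%. Leaving out one: 3/11 = 27.3%. Leaving out two: 2/10 = 20.0%.
- Topical arm, all kept: 8/24 = 33.3%. Leaving out two: 6/22 = 27.3%.
- Two left out of each arm give 20.0% against 27.3%, an apparent difference of 7.3 points where the true difference is zero.
- A sole complication in a stopped nebulizer subject: 1/12 = 8.3% becomes 0/11 = 0%.

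**6. Effect on the planned median and quartiles.** Take assumed cough counts for 12 subjects of 0, 0, 0, 1, 1, 1, 2, 2, 3, 4, 6, 8. The median is 1.5 (quartiles 0.75 and 3.25). Without the two highest counts it is 1 (quartiles 0.25 and 2).

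**The case against.** The strongest reply is that the plan never says withdrawn subjects' data are deleted or excluded, so this is an omission in a descriptive feasibility study with no planned test. Much of that stands, and it rules out several stronger readings.

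- *Safety events are lost.* A reader might infer this from 3.3.1. The documents do not support it: safety data are collected at each procedure (10.3, 10.6), suspension rests on safety data after each subject's bronchoscopy (10.8), and adverse events go on each subject form (20.1.2). Only their place in the comparison is open.
- *Recovery-unit items are forbidden after a stop.* Not stated. Section 7.1 collects them after the procedure without exception, and 7.3 sets participation from consent to discharge readiness without mentioning withdrawal.
- *The heaviest coughers are the ones terminated.* Section 7.1 sends cough that prevents the procedure to a paralytic contingency, not to termination. How that fits with the paralytic exclusion in 3.2 is a separate matter. Safety stops may therefore track cough count only loosely.
- *The rule falls unequally on the arms, or recruits replace failures.* Whether a case abandoned during nebulization counts as a terminated bronchoscopy is not said. Section 3.3.2 says that no need for replacement is anticipated. Swapping is an inference from an unclear clause.
- *The bias can be quantified.* It cannot. With assumed over-dispersed counts (negative binomial, means 4 and 2) and 30% or 60% termination among subjects with six or more severe coughs, the mean difference of 2.0 falls to about 1.7 or to 1.2–1.3. But the plan reports medians. The median difference stays at 2 with gamma shape 2 and falls to 1 with shape 1.

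The reply does not remove the rule itself. Section 3.3.1 says that these subjects leave the study, and leaving them out is a natural way to apply it. Recording an adverse event on a form does not protect the cough endpoint or the recovery-unit outcomes.

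**Conclusion.** The concern holds in limited form. Section 3.3.1 requires a withdrawal after randomisation that can depend on the assigned technique. Section 3.3.2 describes no study follow-up afterwards, and sections 8.1 to 8.3 do not keep the subject in the analysis. Cough counts, recovery-unit items and the between-arm complication summary are exposed to informative loss; the recording of safety events during the procedure is not.

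The firm figures are the weights: 8.3% of a nebulizer arm or 4.2% of the topical arm per subject. The chance of at least one stop among 48, 38.3% to 99.4%, rests on assumed rates of 1% to 10%. The shifted percentages and medians rest on assumed counts and on stopped subjects being left out. The documents do not establish that data are discarded, that stops follow cough, or that one arm is affected more than another.

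**What to change.** Separate stopping the procedure from leaving the study.

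- **3.3.1:** state that early termination of the bronchoscopy, or of lidocaine administration, ends the procedure but not study participation. Limit withdrawal to withdrawn consent.
- **3.3.2:** state that a terminated subject stays in the assigned arm, that coughs counted up to termination are retained, and that adverse events and the recovery-unit cough, sore-throat and discharge-readiness items are collected as for all subjects.
- **8.1:** state that the 48 are all assigned subjects and that none is replaced after the envelope is opened.
- **8.3:** report terminations and their reasons by arm. Show cough results for all assigned subjects, and add a sensitivity summary that ranks subjects terminated because of cough as the highest count. A rank suits the planned medians and an intraoperative outcome that is a count.

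The cost is a short amendment and one field on the subject form for termination and its reason. The recovery-unit items are already planned. The downside is small: some terminated subjects will have a short observation period or missing recovery-unit answers, which should be reported by arm. The sample size stays at 48, and nothing here changes when a procedure is stopped.
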